5.11. Analyses for the Entire Study

The study design includes a 12m-DB period and an OLE period. The primary objective is to evaluate the efficacy and safety of patisiran compared with placebo during the 12m-DB period. In addition, the long-term efficacy and safety of patisiran during the entire patisiran treatment period (beyond 12m-DB) will be characterized for the All Patisiran Treated Set.

The detailed definitions for different treatment periods are as follows.

- **12m-DB Period**

The treatment comparison of patisiran versus placebo will focus on the 12m-DB period, defined as below:

1. For patients who received at least one dose of patisiran during the OLE period, all assessments collected prior to the first dose of patisiran in the OLE period will be included in the 12m-DB period. For patients randomized to patisiran, longitudinal efficacy assessments after the first OLE dose may be included in the 12m-DB period analyses as described in Section 5.6.
2. For patients who discontinued treatment and did not receive any patisiran doses in the OLE period, all assessments will be included in the 12m-DB period. Assessments collected within given time windows (details listed in below table) will be included in summary tables/figures and those outside the time windows will be listed only, unless otherwise specified (eg, AEs in Section 6.9).

Endpoint	Windowing rule for patients who did not enter OLE
Hospitalization/urgent HF visit/death	Events occurring on or before Day 417
Other efficacy endpoints	Assessments collected on or before Day 417
PK/PD endpoints	Assessments collected within 28 days of the last dose
Safety endpoints	Assessments with onset date within 28 days of the last dose ^a

^a In the rare situation where a patient did not discontinue treatment in the 12m-DB period and did not enter the OLE period, all data will be included in the summary tables/figures. For AE summaries, related AEs will be considered treatment-emergent and included in summary tables regardless of time window.

- **OLE Period**

The start day of the OLE period is defined as the day when the first dose of the OLE period is administered. Unless otherwise specified, the assessments collected or AEs with onset date after the administration of the first dose in the OLE period will be included in the OLE period. When assessments or AE onset dates are exactly the date of first dose in the OLE period and the assessment or AE onset time is missing, the records will be included in the OLE period.

- **During Patisiran Treatment**

For all patients who received at least one dose of patisiran, data will be summarized for the “during patisiran treatment” period, defined as below.

1. For patients who received patisiran in the 12m-DB period, all assessments collected after the first dose of patisiran during the entire study, including both the 12m-DB and OLE periods (if available), will be included in the “during patisiran treatment” period.
2. For patients who received placebo in the 12m-DB period and switched to patisiran in the OLE period, all assessments collected after the first dose of patisiran in the OLE period will be included in the “during patisiran treatment” period.
3. For patients who discontinued patisiran treatment during the 12m-DB period, the data handling will follow the same rules as discussed above for “12m-DB period”. For patients who stopped participation in the study during the OLE period, assessments

collected within given time windows (details listed in below table) will be included in summary tables/figures and those outside the time windows will be listed only, unless otherwise specified (eg, AEs in Section 6.9). For ongoing patients, all data will be included.

Endpoint	Windowing rule for patients who discontinued patisiran in the OLE
Efficacy endpoints	Assessments collected within 90 days of the last dose
PD endpoint	Assessments collected within 24 days of the last dose
Safety endpoints	Assessments with onset date within 28 days of the last dose ^a

^a For AE summaries, related AEs will be considered treatment-emergent and included in summary tables regardless of time window.

Longitudinal efficacy parameters will be summarized over the entire study, including the 12m-DB and OLE periods, for all patients to show the long-term efficacy of patisiran (for patients randomized to patisiran) as well as to show the trajectory changes comparing the placebo experience versus the patisiran experience (for patients randomized to placebo). In these summaries, patients will be analyzed according to the treatment to which they were randomized during the 12m-DB period.

6. STATISTICAL ANALYSIS

6.1. Patient Disposition

The number and percentage of patients in the following categories will be summarized by randomized treatment arm and overall, as appropriate:

- Randomized
- Treated
- Completed Month 12 visit
- Discontinued treatment in the 12m-DB period and primary reason for treatment discontinuation and discontinuation due to COVID-19
- Stopped participation in the study in the 12m-DB period and primary reason for stopping participation and stopping participation due to COVID-19
- Entered the OLE period
- Discontinued treatment in the OLE period and primary reason for treatment discontinuation and discontinuation due to COVID-19
- Stopped participation in the study in the OLE period and primary reason for stopping participation and stopping participation due to COVID-19.

The number and percentage of patients enrolled by country and site will be summarized by randomized treatment arm and overall. The number and percentage of patients in each level of each randomization stratification factor as recorded in IRS and in the clinical database, and a

comparison of the number and percentage of patients in each randomization stratification factor in IRS versus the clinical database will be summarized by randomized treatment arm and overall.

6.2. Demographics and Baseline Characteristics

Demographic and baseline characteristics, baseline disease characteristics, baseline efficacy parameters, and medical history information will be summarized by treatment arm and overall. No formal statistical comparisons will be performed.

Age at randomization, height, weight, body mass index (BMI), and mBMI will be summarized using descriptive statistics. Age group, sex, race, ethnicity, region, and country will be summarized by presenting the frequencies and percentages of patients in each category.

The following baseline disease characteristics will be summarized by presenting the numbers and percentages of patients in each category:

- Type of ATTR amyloidosis [hATTR; wtATTR]
- Genotype for hATTR patients
- Baseline tafamidis use [Yes; No]
- NYHA class [I; II; III]
- NYHA class I/II and age at randomization < 75 years [Yes; No]
- ATTR amyloidosis disease stage [1; 2; 3]
- Polyneuropathy disability (PND) score [0; I; II]
- Previous heart failure hospitalization [Yes; No]

The age at symptom onset and the time in years since diagnosis will be summarized, overall and by type of ATTR amyloidosis, using descriptive statistics. For patients who had at least 1 previous heart failure hospitalization, the age at first hospitalization for heart failure and the number of hospitalizations for heart failure in the previous 12 months will be summarized using descriptive statistics. For those who previously used tetramer stabilizers, the time from discontinuation of tetramer stabilizer to the start of study drug will be summarized using descriptive statistics. For patients in the baseline tafamidis group (per the clinical database), the time from the start of tafamidis therapy to the start of study drug will be summarized using descriptive statistics.

The number and percent of patients with each type of ATTR amyloidosis and with each genotype (for hATTR patients) will be summarized by country and treatment arm.

Medical history will be summarized by system organ class (SOC), high level term (HLT), and preferred term (PT). A patient contributes only once to the count for a given condition (overall, by SOC, by HLT, by PT).

All demographic and baseline data for each patient will be provided in data listings. Medical history data including general medical history, cardiac medical history, neuropathy history, historical inpatient admissions or urgent healthcare visits in the past 12 months, and ophthalmic medical history will be presented in data listings. Screening test results will also be presented in data listings.

6.3. Protocol Deviations

A protocol deviation is any change, divergence, or departure from the study design or procedures defined in the clinical protocol. Protocol deviations will be classified by medical review prior to the final 12m-DB analysis, and major protocol deviations will be identified. A major protocol deviation is a deviation that may significantly impact the completeness, accuracy, and/or reliability of the trial data; that may significantly affect a subject's rights, safety, or well-being. (ICH. E3 R1 Structure and Contents of Clinical Study Reports Guidance for Industry. 2013) All major deviations related to trial inclusion or exclusion criteria, conduct of the trial, patient management or patient assessment will be described in the clinical study report.

The Sponsor or designee will be responsible for producing the protocol deviation file (formatted as a Microsoft Excel file). This file will include a description of each protocol deviation and whether or not this deviation is classified as a major protocol deviation. Since the study will be ongoing at the time of the primary analysis, there will be continuing review of protocol deviations. The file with all protocol deviations through the prespecified cutoff date for the final 12m-DB analysis will be finalized prior to the interim lock of the database and study unblinding. After the study is completed, the file with all protocol deviations for the study will be finalized prior to the hard-lock of the database.

All protocol deviations, COVID-19-related protocol deviations, and major protocol deviations will be summarized.

6.4. Drug Exposure

Exposure to study drug in months and the number of doses of study drug received will be summarized by treatment arm. Summaries of the numbers and percentages of patients with no missing infusions, and the number of missing infusions per patient will also be provided. The total drug exposure will also be summarized.

The last date of exposure to study drug is defined as the earliest day of the following dates:

- Last dose date + 20 days
- Analysis cutoff date
- End of study date

Duration of exposure is defined as (the last date of exposure to study drug – date of the first dose +1)/30.4375. The exposure during the 12m-DB period is right censored by the date of the first OLE dose, ie, the last exposure day in the 12m-DB period is no later than the day before the first OLE dose. Similarly, the exposure during the OLE is left censored by the date of the first OLE dose, ie, the Day 1 of the OLE is the day of the first OLE dose. Dose interruptions and compliance are not taken into account for duration of exposure.

Study drug exposure data collected in the eCRFs of study drug administration will also be summarized for each infusion. The numbers and percentages of patients with complete, partial, and missing dose administrations will be summarized. Complete and partial administration is defined as follows:

- Complete: $\geq 80\%$ (≥ 160 mL) of the planned infusion volume (200 mL)

- Partial: >0% to <80% (>0 to <160 mL) of the planned infusion volume (200 mL).

The number of patients who experienced interruptions of infusions for any reason will be tabulated, as well as the number of patients with infusion interruptions due to an infusion-related reaction (IRR).

Dosing information for each patient will be presented in a data listing.

6.5. Premedications

All patients will receive premedications in order to reduce the potential of an IRR. Premedications will be coded using the WHO Drug Dictionary (March 2019 or later). Results will be tabulated by anatomical therapeutic class (ATC) and preferred term.

Premedication data will be presented in a data listing.

6.6. Efficacy Analyses

Efficacy endpoints will be analyzed using the FAS.

6.6.1. Primary Endpoint

The primary efficacy endpoint is to compare the change in 6-MWT from baseline to Month 12 between treatment arms.

6.6.1.1. Definition of Estimand

For the objective of evaluating the efficacy of patisiran compared with placebo on 6-MWT, the estimand is defined as follows:

- **Target patient population:** patients with hATTR or wtATTR amyloidosis with cardiomyopathy. Patients may or may not be taking tafamidis at study entry.
- **Treatment condition:** Patisiran 0.3 mg/kg or placebo administered as an IV infusion q3W (once every 3 weeks) with or without concomitant use of tafamidis.
- **Endpoint:** Change from baseline in 6-MWT at Month 12.
- **Population-level summary:** The stratified Hodges-Lehmann (HL) estimate of the median difference in the change from baseline in 6-MWT at Month 12 between the patisiran and placebo arms. The *p* value for the treatment difference will be estimated using the stratified Wilcoxon Rank Sum test.

Intercurrent events and strategies: Intercurrent events include treatment discontinuation, serious COVID-19 AE, tafamidis drop-in, missing dose(s) due to COVID-19, inability to walk due to progression of ATTR amyloidosis, and death. They require different handling strategies, which are described in [Table 1](#) below.

Table 1: Intercurrent Event Strategies for the Primary Analysis of 6-MWT

Intercurrent Event	Handling Strategy
Treatment discontinuation (not due to death)	Treatment policy strategy: Intercurrent event is ignored; 6-MWT assessments obtained after treatment discontinuation will be included in analysis.
Serious COVID-19 AE	Hypothetical strategy: Assessments obtained on or after the onset of a serious COVID-19 AE will be treated as missing and will be assumed as MAR. The goal is to estimate the scheduled visit values as if the patient had not been infected with COVID-19.
Tafamidis drop-in (ie, taking tafamidis for more than 28 days after randomization) in the subgroup of patients who were not on tafamidis at baseline	Treatment policy strategy: Intercurrent event is ignored; 6-MWT assessments obtained after tafamidis drop-in will be included in analysis.
Missing dose(s) due to COVID-19	Treatment policy strategy: Intercurrent event is ignored; 6-MWT assessments obtained after missing dose(s) due to COVID-19 will be included in analysis.
Inability to walk due to progression of ATTR amyloidosis (including patients who are unable to walk due to hospitalization related to progression of ATTR amyloidosis) ^a	Composite variable strategy: For patients who are unable to walk due to progression of ATTR amyloidosis, the missing Month 12 6-MWT change from baseline will be imputed as the worst 10 th percentile change observed across all patients in the 12m-DB period, capped by the worst possible change for the patient (ie, 0 – baseline 6-MWT).
Death (including heart transplant and ventricular assist device placement) not due to COVID-19 ^a	Composite variable strategy: For patients who die (not due to COVID-19), the missing Month 12 6-MWT change from baseline will be imputed as the worst 10 th percentile change observed across all patients in the 12m-DB period, capped by the worst possible change for the patient (ie, 0 – baseline 6-MWT).
Death due to COVID-19	Hypothetical strategy: Missing data due to COVID-19 death will be assumed as MAR.

^a The imputed outcome will be used in the stratified Wilcoxon Rank Sum test and stratified HL estimate but will not be used in the descriptive summaries.

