5.8.2. Handling of Missing Data

For 6-MWT, the primary analysis will be based on the stratified Wilcoxon Rank Sum test. For patients with missing data at Month 12 who die during the 12m-DB period (not due to COVID-19) or who have become unable to walk due to progression of ATTR amyloidosis by Month 12, the missing Month 12 6-MWT change from baseline will be imputed as the worst 10th percentile change observed across all patients in the 12m-DB period, capped by the worst possible change for the patient (ie, 0 – baseline 6-MWT). Missing data due to other reasons will be multiply imputed assuming data are missing at random (MAR). Data handling strategies for intercurrent events in the primary analysis of 6-MWT are detailed in [Table 1](#). Sensitivity analyses for 6-MWT will be conducted to assess the impact of missing data as discussed in [Section 6.6.1.3](#).

For KCCQ-OS, the primary analysis will be based on the mixed-effects model repeated measures (MMRM) method, which makes use of fully and partially observed data sequences from individual patients by estimating the covariance between data from different time points. The MMRM will be implemented using an unstructured approach to modeling both the treatment-by-time means and the (co)variances, leading to what is essentially a multivariate normal model wherein treatment arm means at the primary time point are adjusted to reflect both the actually observed data and the projected outcomes from the patients with missing data. [[Mallinckrodt 2008](#)] Data handling strategies for intercurrent events in the primary analysis of KCCQ-OS are detailed in [Table 3](#). In this primary analysis, missing data will not be explicitly imputed and are assumed to be MAR. Sensitivity analyses for KCCQ-OS will be conducted to assess the impact of missing data as discussed in [Section 6.6.2.1.3](#).

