6.6.1.2. Primary Analysis using the Stratified Wilcoxon Rank Sum Test and Hodges-Lehmann Estimate

The primary analysis will be performed using the stratified Wilcoxon Rank Sum test for the FAS, stratified by baseline tafamidis use (yes vs. no). The analysis will be based on the following assumptions for missing data at Month 12:

1. Patients who die during the 12m-DB period (not due to COVID-19) or who have become unable to walk due to progression of ATTR amyloidosis by Month 12 and have missing data: Assuming that deaths observed in the study will likely be related to worsening of disease, the missing Month 12 6-MWT change from baseline will be imputed as the

worst 10th percentile change, capped by the worst possible change for the patient (ie, 0 – baseline 6-MWT).

2. Patients who have missing data due to other reasons will be imputed assuming data are MAR. Since the pattern of missing data within patients may be non-monotone, multiple imputation will be conducted separately by treatment arm and baseline tafamidis use group using the Markov Chain Monte Carlo (MCMC) method. For each treatment arm/baseline tafamidis use group, the imputation model will include type of amyloidosis (hATTR vs. wtATTR), NYHA class (I/II vs. III), age at randomization (<75 vs. ≥75), baseline NT-proBNP (≤3000 ng/L vs >3000 ng/L), baseline 6-MWT, and all calculated values of change from baseline in 6-MWT at pre-specified visits.

Missing values will be imputed 100 times to generate 100 complete datasets using the procedures described above. The stratified Wilcoxon Rank Sum test will be applied to each imputed dataset for the change from baseline in 6-MWT at Month 12. The Z scores estimated from the stratified Wilcoxon Rank Sum test fit to each imputed dataset will be combined by applying Rubin's rules,[Rubin 1996; Rubin 1987] using SAS PROC MIANALYZE to produce inferential results for the *p* value.

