Heart transplantation and ventricular assist device placement	Composite variable strategy: Heart transplantation and ventricular assist device placement will be treated in the same manner as death.

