9. APPENDICES

9.1. Detailed Statistical Methodology for the Control-based Imputation for Missing Data

Patients are classified into five patterns for missing data at Month 12:

1. Patients who have missing data due to COVID-19: missing data will be assumed to be MAR and imputed by using MI estimated from the treatment arm and baseline tafamidis use group to which the patient was randomized. This pattern includes:
 - a. Patients who miss the Month 12 assessment due to COVID-19
 - b. Patients who have a serious COVID-19 AE or who die due to COVID-19 before Month 12
2. Placebo patients who do not have missing data due to COVID-19 and are alive through the 12m-DB period and have not become unable to walk due to progression of ATTR amyloidosis by Month 12: missing data will be assumed to be MAR and imputed by using MI estimated from placebo patients in the baseline tafamidis use group to which the patient belongs.
3. Patisiran patients who do not have missing data due to COVID-19 and are alive through the 12m-DB period, have not become unable to walk due to progression of ATTR amyloidosis by Month 12, and have missing data with the last dose of study drug received within 60 days of the scheduled time point: missing data will be assumed to be MAR and imputed by using MI estimated from on-treatment patisiran patients in the baseline tafamidis use group to which the patient belongs.
4. Patisiran patients who do not have missing data due to COVID-19 and are alive through the 12m-DB period, have not become unable to walk due to progression of ATTR amyloidosis by Month 12, and the last dose of study drug was received more than 60 days prior to the scheduled time point: missing data will be assumed to be MNAR and imputed (using data from placebo patients in the baseline tafamidis use group to which the patient belongs) using the copy reference (CR) approach.
5. Patients who die (including heart transplant and ventricular assist device placement) during the 12m-DB period (not due to COVID-19) or who have become unable to walk due to progression of ATTR amyloidosis by Month 12: missing data will be assumed to be MNAR and imputed as the worst 10th percentile change observed across all patients in the 12m-DB period, capped by the worst possible change for the patient (ie, 0 – baseline 6-MWT).

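### Heart transplant and VAD are classed with death for the primary 6-MWT analysis, but the rule replaces only a missing Month 12 value, so a walk observed after the procedure is analysed

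*SAP*

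**What the plan says.** All references are to SAP Amendment 2.1.

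- **Section 6.6.1.1, Table 1, event.** The row is "Death (including heart transplant and ventricular assist device placement) not due to COVID-19", and its strategy is composite variable.
- **Table 1, rule for that row.** "For patients who die (not due to COVID-19), the missing Month 12 6-MWT change from baseline will be imputed" with the worst 10th percentile change, capped at 0 minus the patient's baseline.
- **Section 5.8.2.** The sentence begins "For patients with missing data at Month 12 who die during the 12m-DB period (not due to COVID-19". It names deaths and inability to walk, but not transplant or VAD.
- **Section 6.6.1.2.** "The analysis will be based on the following assumptions for missing data at Month 12" introduces the list. Item 1 covers patients who die or are "unable to walk due to progression of ATTR amyloidosis by Month 12 and have missing data". Transplant and VAD are again not named. Item 2 imputes all other missing values under MAR.
- **Section 6.6.1.3, Sensitivity Analysis 2, item 3.** Same condition as Section 6.6.1.2, item 1.
- **Section 9.1.** "Patients are classified into five patterns for missing data at Month 12". Pattern 5 names transplant and VAD, but sits inside that list.
- **Section 6.6.2.2.1, Table 4 (win ratio).** "Heart transplantation and ventricular assist device placement will be treated in the same manner as death". Table 5 does the same for the Andersen-Gill composites, and Section 6.6.2 counts both procedures as deaths for the secondary endpoints.

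**The concern.** For a true death the word *missing* does almost no harm, because no Month 12 walk normally exists. Transplant and VAD differ: the patient can be alive, attend Month 12 and complete a valid walk. The imputation rule then never starts, and nothing else in the SAP sets the walk aside.

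Two things are at stake. First, the primary estimand names a composite strategy that its operative rule does not deliver for these patients. Someone the plan defines as a failure can rank among the better walkers. Second, the hierarchy is inconsistent for one and the same patient: possibly a good result in test 1 (6-MWT), and a death in test 3 (win ratio) and in tests 4 and 5 (Andersen-Gill), test 4 applying if the patient was not on tafamidis at baseline. The event is foreseen, since Section 6.9.1 plans a listing of patients who had either procedure.

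**Working it through.** **Text.** The question is whether any sentence voids a 6-MWT observed after transplant or VAD.

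1. Table 1, 5.8.2, 6.6.1.2, 6.6.1.3 item 3 and 9.1 pattern 5 each depend on a missing Month 12 value. None overrides an observed one.
2. When the SAP means to discard observed walks it says so. The serious COVID-19 AE row of Table 1 declares assessments from onset onward to be missing. The transplant/VAD row has no such sentence.
3. Section 9.1 drops pattern 5 data from the imputation input, but pattern 5 exists only among patients with a missing Month 12 value, so it does not reach a patient who walked.

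**The plan's own figure.** Inputs from Section 5.1: 300 patients (150 per arm), SD 75 m, effects 33 m and 20 m with 70/30 weights.

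- Weighted effect: 0.7 × 33 + 0.3 × 20 = 29.1 m; the SAP uses about 29 m.
- Expected Z: 29 / (75 × √(2/150)) = 29 / 8.66 = 3.35.
- Power: 0.918 (normal), 0.916 (t), 0.905 with Wilcoxon efficiency 3/π. The stated figure of more than 90% is reproduced, and this point does not change it.

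**Effect of one patient, by hand (unstratified).** SD of the rank sum = √(150 × 150 × 301 / 12) = 751. Suppose one patient ranks 285 instead of 30 of 300. The patient passes 255 others. Same-arm patients who are passed each lose one rank, so the arm's rank sum changes only by the opposite-arm patients passed: 255 × 150/299 ≈ 128. The shift in Z is 128 / 751 ≈ 0.17, or about 0.51 for three such patients in one arm.

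**Simulation of the stratified test.** Assumptions not in the SAP: normal changes, placebo mean change −30 m, all k affected patients in one arm and in the stratum without baseline tafamidis, observed post-procedure change of 0, +50 or +100 m. There were 105 + 45 patients per arm and 1,500 simulated trials per scenario. The alternative value was the pooled worst 10th percentile; the individual cap and multiple imputation were not modelled. The table gives the result with the observed walk minus the result with the composite value, across 0 to +100 m.

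| Affected patients | Arm | Shift in Z | Shift in HL estimate (m) |
|---|---|---|---|
| 1 | patisiran | +0.10 to +0.16 | +0.9 to +1.8 |
| 1 | placebo | −0.08 to −0.17 | −1.1 to −1.8 |
| 3 | patisiran | +0.31 to +0.49 | +2.8 to +5.5 |
| 3 | placebo | −0.25 to −0.50 | −3.3 to −5.4 |

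The hand figure of 0.17 sits at the upper end of the simulated range, as expected for a patient moved almost from one end of the ranking to the other.

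**The case against.** The best defence is that the intent is plain. Table 1 and pattern 5 put both procedures inside death, the strategy is labelled composite, and the secondary endpoints treat them as deaths. A programmer who took that label seriously would not carry a walk recorded after a nominal death. The events may also be few, and they must come early enough in a 12-month period for the patient to complete a valid Month 12 walk. Where the patient does not, the value is missing and the Table 1 rule works.

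Most of this stands as to intent and size. It does not repair the text: no sentence voids the observed walk, and the COVID-19 row shows how the SAP writes that instruction when it wants it.

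Three stronger readings are tempting, and the documents do not support them.

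- *The treatment-policy row orders the analyst to keep the walk.* That row does say "6-MWT assessments obtained after treatment discontinuation will be included in analysis", but it is limited to discontinuation other than by death, and the same table counts transplant and VAD as death. The gap lies in the missing-value condition, not in that row.
- *Step 3 of the win ratio also needs repair.* Step 1 normally decides any pair with a transplant or VAD patient, because the procedure counts as death. The exception is a partner whose survival follow-up ends before the procedure.
- *One patient can move Z by a third of a unit.* Dividing the patient's own rank change by the SD gives 255 / 751 = 0.34, but ignores the same-arm patients who lose a rank. The correct figure is about half.

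**Conclusion.** Wrong as written, minor in severity. Followed literally, the primary 6-MWT rule analyses a living transplant or VAD patient with the observed post-procedure walk. That contradicts the composite strategy named in the same row and the way the secondary composites count that patient.

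Under the simulation's assumptions, each such patient shifts Z by about 0.1 to 0.2 and the Hodges-Lehmann estimate by about 1 to 2 m toward that patient's arm. With an assumed 0 to 3 such patients, all in one arm, the total shift in Z is 0 to about 0.5, against an expected Z of about 3.3 and a critical value of 1.96. The SAP gives no expected number of events; if there are none, nothing changes.

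A reader might infer that the primary result is unreliable, or that the sponsor chose not to count these procedures as failures. Neither follows: the intended strategy is stated, the direction of the shift depends on which arm the patients are in, and the likely number is unknown. The point rests on the contradiction in the primary estimand, not on its size.

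**What to change.** In Table 1 and in Sections 5.8.2, 6.6.1.2, 6.6.1.3 (Sensitivity Analysis 2, item 3) and 9.1 (pattern 5), state that for patients with heart transplant or VAD placement on or before the Month 12 assessment, the Month 12 change takes the composite value (worst 10th percentile change, capped at 0 minus baseline) whether or not a later walk was recorded. Name transplant and VAD in 5.8.2 and 6.6.1.2, where they are absent now. Add that walks after the procedure do not enter the imputation model. Sensitivity Analysis 1 inherits the change through Section 6.6.1.2. The win-ratio steps can stay as they are.

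The cost is about one sentence per section and one derivation flag. Sample size, power and data collection are unaffected.
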